5.4. General Concomitant Medications and Supportive Care Guidelines

Subjects should receive full supportive care, including transfusions of blood and blood products, antibiotics, antiemetics, corticosteroids (see section 6.2), etc when appropriate.

6. DOSE DELAYS/DOSE MODIFICATIONS

6.1. Radiation Therapy

A range of dose-fractionation schemes is available to the treating radiation oncologist as part of this study. Most treated lesions will not require deviations in dose from the stated ranges, with some exceptions:

- Brain metastases that develop while the patient is enrolled in this study may be treated with single fraction stereotactic radiosurgery or 3 Gy X 10 fractions as indicated.
- If only less conformal techniques are available to a patient for the treatment of vertebral lesions and the spinal cord will receive the full prescription dose, lower dose regimens of 4 Gy in 5 fractions or 3 Gy in 10 fractions are permissible in order to avoid toxicity.

For every patient, the total dose, dose per fraction, and number of fractions in every course of radiation therapy that the subject receives will be recorded.

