5. TREATMENT PLAN

5.1. Initial Radiation Therapy

5.1.1 Dose-fractionation: The initial course of radiation therapy will be administered in 3 or 5 fractions over 3-21 days, at a recommended dose of 6-12 Gy per fraction for 3 total fractions (total dose 18-36 Gy) or 4-10 Gy per fraction for 5 total fractions (total dose 20-50 Gy). Dose-fractionation schemes with a lower BED will be favored, with the exception of situations in which improved local control to palliate symptoms is also a priority for a given patient. Higher BED regimens may also be considered for larger size tumors and more rapidly growing tumors.

5.1.2 Targeted Site: Visceral metastases or metastases in organs involved in the immune system (e.g. liver, lymph nodes) will be targeted preferentially. If a bone or brain metastasis develops while the patient is enrolled in this trial and requires treatment for palliative purposes, we advise also treating a visceral metastasis.

5.1.3 Radiotherapy Technique: Stereotactic body radiation therapy (SBRT) will be the favored treatment delivery technique due to its high conformality to a target volume and avoidance of organs-at-risk (OAR) of toxicity. Other techniques, like 3-dimensional conformal radiotherapy (3DCRT) and intensity modulated radiation therapy (IMRT), will be permitted with the caveat that the patient will, irrespective of technique, undergo CT simulation for treatment planning using SBRT immobilization devices, undergo daily image guidance to confirm the positioning of the tumor prior to treatment, and the plans must meet standard 3 or 5 fraction SBRT dose constraints to normal tissues. The use of 4D-CT and respiratory motion management for treatment planning and delivery are encouraged as necessary.

5.1.4 Treatment Planning: All patients will undergo CT simulation using SBRT immobilization devices. Target volumes (i.e. GTV, CTV, ITV, PTV) will be delineated at the discretion of the treating physician. In general, minimal or no margin should be added

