for microscopic disease extension in this setting, with the focus on covering gross disease plus an appropriate margin to encompass tumor motion and any physical setup uncertainties. OARs should be contoured according to standard guidelines provided by NRG Oncology for clinical trials.⁴⁰ Megavoltage photons of at least 6MV will be used for all treatment plans. Ideally 95% of the planning target volume (PTV) should receive 100% of the prescribed dose, and all OAR constraints detailed in [Appendix B](#) must be achieved in order to minimize the risk of toxicity. In patients receiving multiple courses of radiation therapy, there will be an assumption of no tissue recovery, and the total dose to any organ from the sum of all radiotherapy courses will need to achieve the dose limits for a single course of hypofractionated radiation therapy as described in [Appendix B](#).

5.1.5 Treatment Delivery: The thoracic radiation oncologist or his/her designated physician is required to be present at the console to review the daily CT and projection images prior to each treatment. A brief documentation of the patient set up is required in the treatment monitoring system of each institution by the treating physician.

5.1.6 Coordination of Radiation with Immune Therapy: The first course of radiation will be initiated at any time point between the date of cycle 1 of immune therapy through the date of cycle 2 of immune therapy.

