Appendix B

Dose-Volume Guidelines for Critical Structures for Hypofractionated Radiation Therapy

Structure	3 Fractions	5 Fractions
Cauda Equina	D0.03cc < 25.5Gy, D5cc < 21.9Gy	D0.03cc < 32Gy, D5cc < 30Gy
Spinal Cord	D0.03cc < 22.5 Gy, D1.2cc < 13Gy	Max < 28 Gy, D0.35cc < 22.5 Gy, D1.2cc < 15.6Gy
Total Lung (-CTV)	V20 < 15% , V11 < 37% , D1500cc < 10.5Gy, D1000cc < 11.4Gy	V13.5Gy < 37%, D1500cc < 12.5Gy, D1000cc < 13.5 Gy
Heart	D0.03cc < 30Gy, D15cc < 24Gy	D0.03cc < 38 Gy, D15cc < 32 Gy
Esophagus	D0.03cc < 27Gy, D5cc < 17.7Gy	D0.03cc < 35Gy, D5cc < 27.5 Gy
Brachial Plexus	D0.03cc < 26 Gy, D3cc < 22 Gy	D0.03cc < 32 Gy, D3cc < 30 Gy
Trachea & Ipsiлат Bronchus	D0.03cc < 30Gy, D5cc < 25.8Gy	D0.3cc < 40 Gy, D5cc < 32 Gy
Sacral Plexus	D0.03cc < 24Gy, D5cc < 22.5Gy	D0.03cc < 32Gy, D5cc < 30 Gy

Great Vessels	D0.03cc < 45Gy, D10cc < 39Gy	D0.03cc < 53 Gy, D10cc < 47Gy
Skin	D0.3cc < 33Gy; D10cc < 31Gy	D0.03cc < 38.5 Gy, D10cc < 36.5 Gy
Stomach	D0.03cc < 30Gy, D10cc < 22.5Gy	D0.5cc < 35 Gy, D5cc < 26.5 Gy
Duodenum	D0.03cc < 24Gy, D10cc < 15Gy	D0.5cc < 30Gy, D5cc < 18.3Gy
Bowel	D0.03cc < 34.5Gy, D20cc < 24Gy	D0.03cc < 40 Gy, D20cc < 28.5Gy
Rectum	D0.03cc < 49.5Gy, D3.5cc < 45Gy, D20cc < 27.5Gy	D0.03cc < 55Gy, D3.5cc < 50Gy, D20cc < 32.5Gy
Bladder	D0.03cc < 33Gy, D15cc < 16.8Gy	D0.03cc < 38 Gy, D15cc < 20 Gy
Ureter	D0.03cc < 40Gy	D0.03cc < 45Gy
Penile Bulb	D3cc < 25Gy	D3cc < 30 Gy
Femoral Heads	D10cc < 24Gy	D10cc < 30 Gy
Bile Duct	D0.03cc < 36Gy	D0.03cc < 41Gy
Renal hilum	D15cc < 19.5Gy	D15cc < 23Gy
Rib	D0.03cc < 50Gy, D5cc < 40Gy	D0.03cc < 57 Gy, D5cc < 45Gy
Ipsilateral Kidney	D130cc < 12.3Gy	D130cc < 14.5Gy
Total Kidney	D200cc < 15Gy	D200cc < 18Gy
Liver	D700cc < 17.1Gy	D700cc < 21Gy

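### The vertebral exception in Section 6.1 accepts the entire prescribed dose to the spinal cord without waiving the cord constraints that Sections 5.1.3 and 5.1.4 make mandatory, and Appendix B has no limits for its 10-fraction course

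*Combined protocol and SAP*

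**What the plan says.** Section 6.1 introduces its exceptions with the statement "Most treated lesions will not require deviations in dose from the stated ranges, with some exceptions". One exception covers vertebral lesions when only less conformal techniques are available. It allows, where "the spinal cord will receive the full prescription dose, lower dose regimens of 4 Gy in 5 fractions or 3 Gy in 10 fractions" are chosen, treatment on that basis with the aim of avoiding toxicity. It does not mention Appendix B or any cord limit.

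Three other places bear on the same plan:

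- Section 5.1.3 permits 3DCRT and IMRT, but on condition that, whichever technique is used, "the plans must meet standard 3 or 5 fraction SBRT dose constraints to normal tissues".
- Section 5.1.4 says that all the organ constraints in Appendix B "must be achieved in order to minimize the risk of toxicity". For patients given several courses it adds that "there will be an assumption of no tissue recovery, and the total dose to any organ from the sum of all radiotherapy courses" has to meet the limits for a single course.
- Appendix B gives the spinal cord limits as "Max < 28 Gy, D0.35cc < 22.5 Gy, D1.2cc < 15.6Gy" for 5 fractions and "D0.03cc < 22.5 Gy, D1.2cc < 13Gy" for 3 fractions. It has no column for 10 fractions.

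The stated 5-fraction range in Section 5.1.1 is "4-10 Gy per fraction for 5 total fractions (total dose 20-50 Gy").

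**The concern.** Section 6.1 describes a case in which the cord takes whatever dose is prescribed, while Sections 5.1.3 and 5.1.4 require the cord to stay within fixed limits. Section 6.1 is worded as relief from the dose ranges, not from the organ limits. For 4 Gy x 5 no such relief is needed, because that regimen is the lower end of the range in 5.1.1. The only rule it could depart from is the cord constraint, about which 6.1 says nothing.

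A planner who relies on 6.1 may therefore produce a plan that 5.1.4 forbids, with no text saying which section governs. The question returns at later courses. Section 5.3 calls for further radiation in stable or progressive disease, Section 3.3 sets no maximum number of courses under persistent stable disease, and 5.1.4 sums all courses with no recovery. The table of radiation effects in Section 7.2 lists paralysis among the long-term nerve effects, so the ambiguity is more than editorial.

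**Working it through.** **Inputs.** Regimens from Section 6.1: 4 Gy x 5 and 3 Gy x 10, read as dose per fraction. Cord limits for 5 fractions from Appendix B: Max 28 Gy, D0.35cc 22.5 Gy, D1.2cc 15.6 Gy. Range of biologically effective dose (BED) from Section 2.4: 28-100 for early and 47-217 for late responding tissue.

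**The plan's own figure.** BED = n x d x (1 + d/(alpha/beta)). The documents do not state alpha/beta; 10 and 3 are assumed, and they return the stated ranges:
- 4 Gy x 5: 20 x (1 + 4/10) = 28.0 and 20 x (1 + 4/3) = 46.7.
- 10 Gy x 5: 50 x (1 + 10/10) = 100.0 and 50 x (1 + 10/3) = 216.7.

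**4 Gy x 5, compared directly in Gy.** Total 5 x 4 = 20 Gy.

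| 5-fraction cord limit | Cord dose | Result |
|---|---|---|
| Max < 28 Gy | 20 Gy | met |
| D0.35cc < 22.5 Gy | 20 Gy | met |
| D1.2cc < 15.6 Gy | 20 Gy | exceeded: 20/15.6 = 1.28, 28% over |

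The third line requires at least 1.2 cc of cord at full dose. The documents give neither a cord volume nor a treated length. For an assumed cord cross-section of 0.4 to 1.0 cm², the length needed is 1.2/0.4 = 3.0 cm down to 1.2/1.0 = 1.2 cm.

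**3 Gy x 10.** Total 10 x 3 = 30 Gy. No limit in Appendix B applies directly. The nominal 30 Gy is above all three 5-fraction limits, but those limits were written for a different fractionation. A BED conversion, which the protocol does not prescribe for organ limits, gives a mixed answer at alpha/beta 3:
- Regimen: 30 x (1 + 3/3) = 60.0.
- Max: 28 x (1 + 5.6/3) = 80.3, not exceeded.
- D0.35cc: 22.5 x (1 + 4.5/3) = 56.3, exceeded.
- D1.2cc: 15.6 x (1 + 3.12/3) = 31.8, exceeded.

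At alpha/beta 2 the pattern is the same: 75.0 against 106.4, 73.1 and 39.9, with the D0.35cc comparison close.

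**Cumulative rule.** After 20 Gy in 5 fractions to at least 1.2 cc of cord, the D1.2cc limit is already exceeded before any later course is added. The rule can be computed here, but 6.1 does not say whether that first course is exempt from it. After 30 Gy in 10 fractions there is no stated way to put the course into the sum.

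**The case against.** The strongest reply is that Section 6.1 is a specific exception and overrides the general rule. It addresses exactly the case in which the cord cannot be spared and calls the regimens permissible. Since 4 Gy x 5 lies inside the ordinary range, permission for the cord case is arguably all the bullet adds, and a 10-fraction course cannot have been meant for a table with only 3- and 5-fraction columns. On that view the two rules do not deadlock; an exception was intended but not written out.

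This has force, and a reader who infers that no site could ever use 6.1 goes too far. It does not remove the point. The lead-in to 6.1 limits its exceptions to the dose ranges, no waiver of the cord limits appears, and although Appendix B is titled as guidelines, 5.1.4 makes its limits mandatory. An implied waiver would also leave the cumulative rule unanswered.

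Other stronger readings that the documents do not support:
- That 20 Gy in 5 fractions breaks the cord limits as a set. Two of the three are met.
- That 30 Gy in 10 fractions is shown to breach a limit. None is stated for it; any excess is nominal or rests on an assumed conversion, and the converted Max is met.
- That the cumulative check is undefined throughout. It is undefined only for the 10-fraction course, and Section 5.3 sends later courses to a different, unirradiated lesion, so overlap at the cord is not automatic.
- That 4 Gy might be a total dose. The parallel 10-fraction wording and the 4 Gy lower end in 5.1.1 indicate dose per fraction.

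The reach is also narrow: visceral sites are preferred to bone, SBRT is favoured, and the exception requires that only less conformal techniques be available. No endpoint or analysis depends on it.

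**Conclusion.** The inconsistency holds in a limited form. With at least 1.2 cc of cord at full dose (about 1.2 to 3.0 cm of cord under the assumed cross-sections), 4 Gy x 5 as allowed in Section 6.1 exceeds the D1.2cc limit that 5.1.4 makes mandatory, by 28%; the Max and D0.35cc limits are met. For 3 Gy x 10 the finding is the absence of an applicable limit and of a rule for the cumulative sum, not a demonstrated breach. It affects a small subset of patients, but it concerns a critical organ and two instructions that, as written, cannot both be followed in that case. It should be corrected. No view is taken here on which regimen or limit is right.

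**What to change.** Reconcile Sections 5.1.3, 5.1.4, 6.1 and Appendix B so that they state:

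1. whether the vertebral regimens in 6.1 are subject to the Appendix B cord constraints, D1.2cc included;
2. which limits apply to a 10-fraction course;
3. how a course given under 6.1 counts in the no-recovery cumulative sum when a later course is planned.

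The clinical team decides which rule stands. The cost is a protocol amendment of a few sentences and a footnote to Appendix B; the sample size and the analysis are unaffected.

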6.2. Immune therapy

Appropriate dose modifications for immune therapy agents are at the discretion of the treating medical oncologist, and will be managed according to standard of care. All dose modifications or missed treatments should be recorded for analysis but no specific dose modification parameters will be used since the immune therapy is not the experimental component in this study. For treatment of moderate or severe immune related adverse

events (irAEs), we advise interruption of the checkpoint inhibitor and the use of corticosteroid immunosuppression. For grade 2 (moderate) immune-mediated toxicities, treatment with the checkpoint inhibitor should be withheld and should not be resumed until symptoms or toxicity is grade 1 or less. Prednisone 0.5 mg/kg/day or equivalent should be started if symptoms do not resolve within a week. For grade 3 or 4 (severe or life-threatening) immune-mediated toxicities, treatment with the checkpoint inhibitor should be permanently discontinued. Prednisone 1-2 mg/kg/day or equivalent should be given immediately. When symptoms subside to grade 1 or less, steroids can be gradually tapered over at least one month. If symptoms do not improve within 3 days of starting steroids, administer infliximab 5 mg/kg (may repeat 2 weeks later if no improvement in symptoms). If the immune therapy is withheld for a period of greater than 14 days at a time when a course of radiation therapy was planned to be given, the course of radiation therapy may be initiated prior to resuming the immune therapy.

7. ADVERSE EVENTS

7.1. Definitions

7.1.1. Adverse Event

An adverse event (AE) is any unfavorable or unintended event, physical or psychological, associated with a research study, which causes harm or injury to a research participant as a result of the participant's involvement in a research study. The event can include abnormal laboratory findings, symptoms, or disease associated with the research study. The event does not necessarily have to have a causal relationship with the research, any risk associated with the research, the research intervention, or the research assessments.

Adverse events may be the result of the interventions and interactions used in the research; the collection of identifiable private information in the research; an underlying disease, disorder, or condition of the subject; and/or other circumstances unrelated to the research or any underlying disease, disorder, or condition of the subject; and/or other circumstances unrelated to the research or any underlying disease, disorder, or condition of the subject.

7.1.2. Serious Adverse Events

Serious adverse event (SAE) or serious suspected adverse reaction: An adverse event or suspected adverse reaction is considered “serious” if, in the view of the investigator or sponsor, it results in any of the following outcomes:

- **Death**
- **A life-threatening** adverse experience. The term life-threatening in the definition of serious refers to an adverse event in which the subject was at immediate risk of death at the time of the event. It does not refer to an adverse event which in a more severe form might have caused death.

- Requires **inpatient hospitalization or prolongation of existing hospitalization**. Any adverse event leading to hospitalization or prolongation of hospitalization will be considered as Serious, UNLESS at least one of the following expectations is met:
 - The admission results in a hospital stay of less than 24 hours OR
 - The admission is pre-planned (e.g., elective or scheduled surgery arranged prior to the start of the study) OR
 - The admission is not associated with an adverse event (e.g., social hospitalization for purposes of respite care).

However it should be noted that invasive treatment during any hospitalization may fulfill the criteria of “medically important” and as such may be reportable as a serious adverse event dependent on clinical judgment. In addition where local regulatory authorities specifically require a more stringent definition, the local regulation takes precedent.

- Results in **persistent or significant disability/incapacity or** substantial disruption of a person’s ability to conduct life’s normal functions.
- Is a **congenital anomaly/birth defect**
- Is an **important medical event**. Important medical events that may not result in death, be life-threatening, or require hospitalization may be considered a serious adverse experience when, based upon appropriate medical judgment, they may jeopardize the subject and may require medical or surgical intervention to prevent one of the outcomes listed in this definition.
 - Examples of such medical events include allergic bronchospasm requiring intensive treatment in an emergency room or at home, blood disease or disorders, or convulsions that do not result in inpatient hospitalization, or the development of drug dependency or drug abuse. The development of a new cancer is always considered an important medical event.

7.2. Adverse Event Evaluation

The investigator or designee is responsible for ensuring that all adverse events (both serious and non-serious) observed by the clinical team or reported by the subject which occur after the subject has started immune therapy are fully recorded in the subject’s medical records. Source documentation must be available to support all adverse events. A laboratory test abnormality considered clinically relevant (e.g., causing the subject to withdraw from the study, requiring treatment or causing apparent clinical manifestations, result in a delay or dose modification of study treatment, or judged relevant by the investigator), should be reported as an adverse event.

The investigator or sub-investigator (treating physician if applicable) will provide the following for all adverse events (both serious and non-serious):

- Event term (as per CTCAE version 4.0)
- Description of the event

- Date of onset and resolution
- **Expectedness of the toxicity**
- **Grade of toxicity**
- **Attribution of relatedness to the investigational agent- (this must be assigned by an investigator, sub-investigator, or treating physician)**
- Action taken as a result of the event, including but not limited to; no changes, dose interrupted, reduced, discontinued, etc. or action taken with regard to the event, i.e. no action, received con-med or other intervention, etc.
- Outcome of event

The most common adverse event from the short courses of focal radiation therapy used in this study will be fatigue. This may be accompanied by decreased appetite, changes in taste, or weight loss. Since radiation is a focal, localized treatment to a specific targeted tumor, the likelihood of all other side effects is dependent on the part of the body that is treated, as described in the table below. Unknown side effects may also arise due to the combination of radiation therapy and immunotherapy in this study.

	Acute/Short-Term/Temporary	Chronic/Long-Term/Permanent
Skin	redness, dryness, darkening, itching, peeling, tenderness, hair loss	thickening, firmness, discoloration, hair loss
Bone	decreased blood counts	fracture, pain
Nerves	electrical sensation	pain, loss of strength, numbness, tingling, paralysis
Lymphatics	Swelling	lymphedema
Brain	fatigue, brain swelling, headaches, nausea, vomiting, dizziness, drowsiness, altered taste or smell	loss of strength, numbness, tingling, paralysis
Lungs	cough, shortness of breath, bleeding	cough, shortness of breath, bleeding, decreased lung capacity
Heart	chest pain, pericarditis, abnormal rhythm	chest pain, heart attack, heart failure, pericarditis
Esophagus	difficulty swallowing, painful swallowing, food sticking, heartburn, nausea, vomiting, decreased appetite,	stricture, obstruction, perforation, fistula, bleeding, chest pain
Stomach/ Bowel	nausea, vomiting, fatigue, diarrhea, cramping, decreased appetite	stricture, obstruction, perforation, bleeding, abdominal pain, ulceration
Liver	nausea, vomiting, fatigue, diarrhea	decreased liver function, ascites, cirrhosis, encephalopathy, bleeding
Rectum	spasm, frequent bowel movements	ulceration, bleeding
Bladder	burning/pain with urination, increased frequency, urinary urgency	decreased bladder capacity, bladder spasms, bleeding

Immune therapy agents have their own set of expected side effects, as detailed below.

	Nivolumab	Pembrolizumab	Atezolizumab
Common	Fatigue Decreased appetite	Fatigue Decreased appetite	Fatigue Decreased appetite

	Generalized weakness	Nausea Rash	Lung inflammation Fever
Occasional	Nausea Diarrhea Joint inflammation Fever Lung inflammation Rash	Diarrhea Decreased thyroid hormone levels Increased thyroid hormone levels Lung inflammation Generalized weakness Anemia Mouth/Lip Sores	Nausea Diarrhea Joint inflammation Insomnia Lung Infection Generalized weakness
Rare	Mouth/Lip Sores Muscle inflammation Colon inflammation Anemia Peripheral Neuropathy Decreased white blood cell count Hair Loss Liver inflammation	Hair loss Decreased white blood cell count Colon inflammation Severe rash (skin blistering/ulceration) Pancreas inflammation Decreased adrenal hormone levels Muscle inflammation Liver inflammation Diabetes Mellitus	Myalgia Hair loss Pneumonia Decreased thyroid hormone levels Peripheral neuropathy Neutropenia Muscle inflammation

7.2.1. Adverse Event Grading

Descriptions and **grading scales** found in the NCI Common Terminology Criteria for Adverse Events (CTCAE) version 4 will be utilized for AE reporting.

Grade	Description
0	No AE (or within normal limits).
1	Mild ; asymptomatic or mild symptoms; clinical or diagnostic observations only; intervention not indicated.
2	Moderate ; minimal, local or noninvasive intervention (e.g., packing cauter) indicated; limiting age-appropriate instrumental activities of daily living (ADL).
3	Severe or medically significant but not immediately life-threatening; hospitalization or prolongation of hospitalization indicated; disabling; limiting self-care ADL.
4	Life-threatening consequences; urgent intervention indicated.
5	Death related to AE

